**Figure 1**

Power	n
0.60	80
0.65	90
0.70	100

Assuming a mean cognitive subscale of the BSID-III, an alpha of 0.05, and an SD of 15.

## **7 SAFETY MANAGEMENT**

### **7.1 Clinical Adverse Events**

Clinical adverse events (AEs) will be monitored throughout the study. The main risks are disclosure of private health information (PHI) and study responses and discomfort with answering sensitive questions concerning childhood trauma or depressive symptoms.

### **7.2 Adverse Event Reporting**

Since the study procedures are not greater than minimal risk, SAEs are not expected. If any unanticipated problems related to the research involving risks to subjects or others happen during the course of this study (including SAEs) they will be reported to the IRB in accordance with CHOP IRB SOP 408: Unanticipated Problems Involving Risks to Subjects. AEs that are not serious but that are notable and could involve risks to subjects will be summarized in narrative or other format and submitted to the IRB at the time of continuing review. We will query participants concerning any disclosures of PHI at each study visit. We will only query participants once concerning childhood trauma at the baseline visit and twice concerning depressive symptoms at the baseline and second (final) study visit.

## **8 STUDY ADMINISTRATION**

### **8.1 Data Collection and Management**

All records generated during this study will be kept confidential in accordance with Institutional policies and HIPAA on subject privacy. The Investigator and other site personnel will not use such data and records for any purpose other than conducting the study.

Unique identifiers will be created for each subject in the study. REDCap will be used to store the data. A master list containing PHI and subject ID number will be kept separate from data forms (electronic and paper). The master list will be kept using password-protected files. These files will be encrypted and maintained on the CHOP secure server to ensure security. Participants' information will be stored in the REDCap database and configured to export data without PHI. All de-identified records will be retained forever. De-identified data will be shared with the study sponsor. Stored data and patient identifiers will be kept for 6 years subsequent to the study completion, and possibly longer if required by the sponsor.

Any paper copies of research instruments will be stored using the patient's ID code and will be kept in the department of General Pediatrics at The Children's Hospital of Philadelphia.

All audio and video recordings will be destroyed within three years of data analysis completion.

## **8.2 Confidentiality**

All data and records generated during this study will be kept confidential in accordance with Institutional policies and HIPAA on subject privacy and that the Investigator and other site personnel will not use such data and records for any purpose other than conducting the study with the exception of mandatory reporting requirements for child maltreatment.

No identifiable data will be used for future study without first obtaining IRB approval. The research staff will obtain a data use agreement between the provider (the PI) of the data and any recipient researchers (including others at CHOP) before sharing a limited dataset (PHI limited to dates and zip codes).

## **8.3 Regulatory and Ethical Considerations**

### **8.3.1 Data and Safety Monitoring Plan**

Monitoring of adverse events, mainly disclosure of PHI from medical records and study assessment responses, will be ongoing during the intervention period until all data have been de-identified. Participants will be asked whether they know of any breaches of confidentiality at all contacts with subjects. All non-serious adverse events including disclosure of information will be reported to the CHOP IRB at the time of continuing review and to the funding agency annually. The PI will be responsible for overseeing the monitoring plan. Trained research assistants under the supervision of the Principal Investigator will conduct monitoring of data and safety twice annually.

### **8.3.3 Potential Benefits of Trial Participation**

Parents or guardians of the participants in either arm may not benefit from the digital literacy promotion intervention. Parents and their children may benefit from initiating parent-child reading activity earlier with the potential for improved language development. Information from this study could be used to generate generalizable knowledge to reshape the views on digital literacy initiatives, the ROR program and provide information for other early literacy campaigns such as Philadelphia's Read! By 4th and the Great Start Collaborative's Early to Read Campaign. If results from this study favor the digital book arm, then administrators of the ROR program and other local and national literacy campaigns can encourage the distribution of developmentally appropriate e-books in conjunction with standard books. Nationally, pediatric clinicians may benefit by knowing evidence of whether there is a difference in effectiveness of language development in children who are read to by their parents via digital or standard book. This may have an impact in environments where access to books may be limited by financial, geographical, or time constraints on parents. Locally, pediatric clinicians could benefit by having CHOP's ROR program expanded to additional areas in the Philadelphia metropolitan area. Information from this study can be used by policymakers and grant funders to increase funding support to expand the ROR program and other local and national literacy campaigns to infants.

### **8.3.4 Risk-Benefit Assessment**

The risks to participants are minimal and further minimized through protections. The benefits of parents receiving advice and materials through the support of the digital literacy promotion program outweigh the risks of participation. Therefore, the risk-benefit ratio is considered favorable.

## **8.4 Recruitment Strategy**

### **8.4.1 Randomized Control Trial**

We will have an EHR recruitment prompt sent only to potentially eligible children with Medicaid at their 4 month well visit at the CHOP Primary Care Roxborough, PA, CHOP Primary Care Cobbs Creek and CHOP Primary Care Indian Valley. Parents who are conceivably interested in participating will be contacted by research staff. Research staff will briefly explain the study procedures, guided by the information set forth in the approved consent form. This includes reading the inclusion criteria to the potential participant, and asking whether or not this individual is interested in participating. Research staff will then schedule a time to meet with the parent in person. This will happen at a time before their infant's 6 month well visit in order to obtain informed consent, confirm that all of the inclusion criteria are met, and randomize the

participant into either the digital or standard book group. In the event that the research staff is unable to confirm that all inclusion criteria are met after the participant has been enrolled, the participant will no longer be able to participate. Additionally, potentially eligible 5 to 7 month olds that have been identified by study staff on EPIC as potentially eligible by screening via review of the medical record, may be approached in person before or at the time of their 6 month well visit. These potentially eligible participants will be screened, consented and enrolled into the study prior to the child's time with the provider.

We may also hang recruitment flyers in the hallways at both clinics giving information about the study and contact information for the study coordinator in case they are interested and we miss their names in the screening process.

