## **3 INVESTIGATIONAL PLAN**

### **3.1 General Schema of Study Design**

#### **3.1.1 Randomized Control Trial**

We propose to test the effects of digital versus standard literacy promotion using a randomized controlled trial design. One-hundred eligible parent-child dyads, with infants between 5 and 7 months of age, who present to one of the three CHOP Care Network practices (Cobbs Creek, Roxborough and Indian Valley) will be recruited and consented to participate in this 18-month long study. Participants will be stratified by clinic site and randomized to receive literacy promotion using 1) standard early reader board books or 2) digital electronic early reader e-books. Randomization sequences will be developed by the study team using computer-generated random numbers prior to study enrollment and will be placed in sealed opaque envelopes.

Randomization will ensure equivalence between groups on measured and unmeasured characteristics and is considered to be the strongest protection against bias in study design.

Participants randomized to the digital arm will receive the e-book version of [name] *Hop on Pop* for the 6 month well visit, Sandra Boynton's *Barnyard Dance* for the 9 month well visit, and Margaret Wise' *Goodnight Moon* for the 12 month well visit. Additionally they will receive information on the importance of early parent-child reading activity by pediatric clinicians using the Reach Out and Read framework. The appropriate e-books will be electronically gifted to the participants. Parents must have an appropriate mobile digital device such as a smart phone or tablet to download and open the digital e-books.

Participants randomized to the standard arm will receive the board book versions of [name] *Hop on Pop* for the 6 month well visit, Sandra Boynton's *Barnyard Dance* for the 9 month well visit, and Margaret Wise' *Goodnight Moon* for the 12 month well visit. Furthermore, participants will be provided information on the importance of parent-child reading activity by pediatric clinicians using the Reach Out and Read framework.

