Written informed consent will be obtained in person prior to any study related procedures being performed. The consenting process will include a discussion of study rationale, procedures, measures, benefits, risks, and alternatives to participation. After consent, subjects will either be assigned to the digital literacy arm or the standard literacy arm of the study. Regardless of their assignment, once they have consented to participate, they will complete a demographic questionnaire (Appendix 1), questionnaires about adverse childhood experiences (Appendix 2) and health literacy (Appendix 3), and the Edinburgh Postnatal Depression Scale (EPDS) (Appendix 4).

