### **3.1.4 Randomized Controlled Trial Treatment Phase (start of the study intervention)**

Once recruited and enrolled, the parent-child dyads will be randomized into either the digital or standard literacy arm. Parent-infant dyads randomized to the digital literacy arm will receive the digital e-book version of [name] *Hop on Pop* for the 6 month well visit, Sandra Boynton's *Barnyard Dance* for the 9 month well visit, and Margaret Wise' *Goodnight Moon* for the 12 month well visit. Moreover, they will receive information on the importance of early parent-child reading activity by pediatric clinicians. Information on early literacy will be standardized and age-based and will be provided to parents by pediatric clinicians at the well visits.

Parent-infant dyads randomized to the standard literacy arm will receive [name] *Hop on Pop* for the 6 month well visit, Sandra Boynton's *Barnyard Dance* for the 9 month well visit, and Margaret Wise' *Goodnight Moon* for the 12 month well visit. In addition, they will be provided information on the importance of parent-child reading activity by pediatric clinicians.

Information on early literacy will be standardized and age-based and will be provided to parents by pediatric clinicians at the well visits. This conforms to the ROR National Program recommendations and is considered standard of care at these 3 clinics.

To prevent contamination in which pediatric clinicians inadvertently provide books and instruction on reading activity to the different arms of the study, an automated alert will appear on the screen of the eligible child's EHR at each well visit with a reminder to the health professional. This will ensure that books and reading instructions are consistent with their assigned study arm. Phone call or text message reminders will be used throughout the course of the study. The initial reminder will be made within the first week to participants in the digital literacy arm to verify that the participant was able to download the e-book if this was not already confirmed during the initial visit. Another reminder will be sent out about 1 month after the infant has, or is age-eligible for, their 6, 9 and 12 month well visit, either to remind the participant to complete the emailed REDCap survey, or for other study-related reminders.

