### **3.4 Study Population**

#### **3.4.1 Randomized Control Trial**

##### **3.4.1.1 Inclusion Criteria**

- 1) English or Spanish speaking
- 2) Child who is between 5 months 0 days and 7 months 0 days at time of enrollment and born  $\geq$  35 weeks estimated gestational age.
- 3) Parent (if mother) must be 15 years or older at the start of the study. Parent (if father) must be 18 years or older at the start of the study.
- 4) Parental permission for the child's participation and consent of the parent for their participation
- 5) Child with Medicaid Insurance

- 6) Parent has access to a smartphone and/or tablet

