### 6.3 Statistical Methods

Summary statistics will be obtained, and differences between digital and standard arms will be assessed using intention-to-treat analysis. Cross-sectional differences in StimQ scores between digital and standard groups at the 6, 9 and 12 month well visits will be assessed using t-tests. To determine how the effects of digital versus standard literacy is associated with language development, we will develop regression models using longitudinal data methods that adjust for correlation in BSID-III scores over time and for potential confounding by demographic characteristics. To explore the impact of digital literacy on healthcare utilization, the EHR will be reviewed to identify a subjects' number of well visits and their vaccination history.

To determine whether parent adversity, health literacy, and/or parent mental health modify the effects of digital versus standard literacy on language development, we will develop similar regression models using longitudinal data methods, but we will also fit interaction terms between study group and ACE score ( $\geq 4$ ), SAHL (high or low) and EPDS score ( $> 10$ ). To determine if parent-child reading activity mediates the association of intervention group assignment and language development, we will use mediation analysis with separate models regressing group assignment on language development, parent-child reading activity on group assignment, and group assignment on language development adjusted for parent-child reading activity.

Assuming a mean cognitive subscale on the BSID-III of 96, a power of 0.70, an alpha of 0.05, and a clinically significant difference of 7.5 points on the BSID-III between groups, we estimate that we will need to recruit a total sample size of 100 eligible children (50 in each group) to participate in the main RCT study (Figure 1). To attain thematic saturation in the Video Sub-study, we will recruit up to 40 participants 9-12 months of age. These 40 participants may be recruited external to the main study if we are unable to recruit up to 40 from the 100 enrolled in the main study in a timely fashion. All analyses will be conducted using Stata Statistical Software, version 13 (College Station, TX).

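### The rule ending participation when eligibility cannot be confirmed after enrolment can reach randomised dyads, possibly unequally by arm, and is not reconciled with the intention-to-treat analysis

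*Combined protocol and SAP*

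**What the plan says.** **Removal rule.** Section 8.4.1 describes a meeting before the 6-month well visit at which staff obtain consent, "confirm that all of the inclusion criteria are met, and randomize the" participant. It then provides that, where staff are "unable to confirm that all inclusion criteria are met after the participant has been enrolled, the participant will no longer be able to participate". The sentence names no arm, sets no time limit, and does not say what happens to data already collected or to the analysis set.

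**Order of enrolment and randomisation.** Section 3.1.4 states: "Once recruited and enrolled, the parent-child dyads will be randomized into either the digital or standard literacy arm". Section 3.1.3.1 states: "After consent, subjects will either be assigned to the digital literacy arm or the standard literacy arm of the study". The list in 4.1 goes from consent to randomisation to baseline data, with no step between the first two at which eligibility is confirmed.

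**Analysis.** Section 6.3 says that "differences between digital and standard arms will be assessed using intention-to-treat analysis", and 3.1.1 and 3.1.4 say the same in substance. None of them defines the set.

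**Device access.** The criterion in 3.4.1.1 applies to both arms: "Parent has access to a smartphone and/or tablet". The description of the digital arm in 3.1.1 adds a functional requirement: "Parents must have an appropriate mobile digital device such as a smart phone or tablet to download and open the digital e-books". Section 3.1.4 gives the digital arm alone a first-week contact "to verify that the participant was able to download the e-book", unless this was settled at the initial visit.

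**The concern.** An intention-to-treat comparison is protected because every randomised dyad counts in the arm it was assigned to. A rule that can end a dyad's participation after allocation weakens that protection in two ways.

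First, the primary endpoint in 6.1 is the BSID-III at the second study visit. A dyad that has left participation before then would normally have no primary outcome. It may remain in the intention-to-treat set by name, but it contributes nothing, and 6.3 gives no method for missing outcomes.

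Second, the chance of being found ineligible after allocation may differ by arm. Device access is an entry criterion for everyone, but after allocation only digital-arm families are asked to show that something works on their device. Section 3.2 describes no blinding despite its title, so nothing stated would keep staff from knowing the arm when they apply the rule. If losses were unequal and related to development, the arms would no longer be comparable.

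**Working it through.** **Step 1. Can the rule act after randomisation?**

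- For a reading confined to the period before randomisation: 8.4.1 lists confirmation ahead of randomisation, and 3.1.4 puts enrolment ahead of randomisation. A dyad could be enrolled, fail confirmation, and leave without being allocated.
- For a reading that extends past randomisation: 3.1.3.1 and 4.1 leave no step between consent and assignment. Section 3.1.4 contemplates that the e-book download may already be confirmed at the initial visit, so allocation is known by then. Section 8.4.1 also allows dyads to be enrolled at the 6-month visit just before the clinician sees the child, and 4.2 has the clinician hand over the arm's book at that visit. The time available between enrolment and allocation is short, yet the removal rule has no end date.

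The text permits both readings and chooses neither.

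**Step 2. Reproduce the plan's sample size.** Inputs from 6.3 and Figure 1: difference 7.5, SD 15, alpha 0.05, power 0.70. Sidedness is not stated; two-sided is used here because it reproduces the plan.

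- n per arm = 2 × (15/7.5)² × (1.960 + 0.524)² = 8 × 6.17 = 49.4, rounded up to 50, so 100 in total.
- The same formula gives 80 at power 0.60 and 90 at power 0.65, which matches Figure 1. One-sided alpha would give 38 per arm.
- With 50 per arm, the standard error is 15 × √(1/50 + 1/50) = 3.0, and power is Φ(7.5/3.0 − 1.960) = Φ(0.54) = 0.705.

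**Step 3. Power if k dyads are lost from the digital arm only.** The value of k is an assumption.

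- k = 2: power 0.697.
- k = 5: standard error 15 × √(1/50 + 1/45) = 3.08, and power is Φ(7.5/3.08 − 1.960) = Φ(0.473) = 0.682.
- Section 3.3.2 counts recruitment on dyads enrolled and mentions no replacement, so losses would not be made up.

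**Step 4. Shift in the digital-arm mean.** Let D be the amount by which the removed dyads' mean falls below that of the dyads kept. The mean of all 50 is the kept mean minus (k/50) × D, so removal shifts the analysed mean by (k/50) × D. Both k and D are assumptions; a D of 7.5 to 15 is 0.5 to 1 SD.

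- k = 2, D = 7.5: 2/50 × 7.5 = 0.3 points, or 0.3/7.5 = 4% of the target difference.
- k = 5, D = 7.5: 5/50 × 7.5 = 0.75 points.
- k = 5, D = 15: 5/50 × 15 = 1.5 points, or 1.5/7.5 = 20% of the target difference.

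If D is negative, the shift has the same size in the opposite direction.

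**Step 5. Effect on the test when the arms truly do not differ.** With k = 5 and SD 15, the two-sided error rate at nominal 0.05 is 0.057 for D = 7.5 and about 0.078 for D = 15. If every removal precedes randomisation, no between-arm bias arises from this rule and the error rate stays at 0.05.

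**The case against.** The strongest reply is that the plan already has the right order. Section 8.4.1 lists confirmation before randomisation and 3.1.4 lists enrolment before randomisation, so the rule may concern only dyads who have consented but are not yet allocated. That reading is available and may be what the sponsor intends. It stands as a possibility but does not settle the matter, because 3.1.3.1 and 4.1 omit the confirming step and the rule has no end point.

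A reader might infer that the rule contradicts the intention-to-treat analysis. The documents do not go that far. Ending participation is not the same as deleting a dyad from the analysis, and the plan is silent on the second. What remains is an undefined analysis set and a probable missing outcome.

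A reader might also infer that dyads would be removed from the digital arm only, through failed downloads. The rule names no arm and covers every inclusion criterion, most of which have nothing to do with the book format. Having access to a device is not the same as completing a download. The contacts described in 1.2, 3.1.4 and 5.1.9 read as support for the intervention, and no section treats a failed download as ineligibility. Unequal removal is therefore a possibility created by unequal checking, not a stated procedure.

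Finally, the illustrative numbers have no source in the documents. That objection stands in full.

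**Conclusion.** The point holds as a gap that should be closed. The removal rule can reach randomised dyads, and the plan does not say how they would be followed or analysed. Because checking after allocation differs by arm, removal could be unequal, with a device problem more likely to come to light in the digital arm.

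The size cannot be known from the documents. The shift of 0.3 to 1.5 points rests wholly on assumed counts (2 to 5 of 50) and assumed score differences (7.5 to 15 points), and its upper end combines the largest value of each. The documents do not support saying that the result would be biased in favour of e-books: that holds only if the families removed would have scored lower. The loss of power is minor, and the sample size of 100 needs no correction on this account. If the sponsor intends removal before randomisation only, the bias disappears and the remedy is to say so.

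**What to change.** In 8.4.1, 3.1.3.1 and 4.1:

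- Require every inclusion criterion, including device access, to be checked and documented before the envelope is opened, in the same way for all dyads.
- Limit the removal rule to dyads not yet randomised.

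For randomised dyads later found ineligible, with matching text in 6.3:

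- Report the violation, as the general statement at the end of 3.4.2.2 requires. That statement also bars enrolment of anyone who fails a criterion, so the new text should be reconciled with it.
- Still seek the BSID-III if the parent agrees and IRB policy allows.
- Define the intention-to-treat set as all randomised dyads, analysed in the assigned arm.
- Report the number found ineligible by arm, and add a sensitivity analysis without them.

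The cost is protocol wording, a checklist used before allocation, and a check against IRB policy. The downside is that a few ineligible dyads may remain in the primary analysis and slightly dilute the effect.
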